Table 3.	Notable Abnormalities of Vital Signs	28

List of Appendices

Appendix A.	Handling of Dates, Incomplete Dates and Missing Dates for Adverse Events and Concomitant Medications	25
Appendix B.	Laboratory Grading and Notable Vital Sign Values	27

Table of Abbreviations

Term or Abbreviation	Description
BM	Bone Marrow
CDM	Clinical Data Management
CSR	Clinical study report
CRF	Case Report Form
EOI	Event Of Interest
E-R	Exposure-Response
IBG	Independent Biostatistics Group
IPD	Important Protocol Deviation
KM	Kaplan-Meier
MedDRA	Medical Dictionary for Regulatory Activities
SAP	Statistical Analysis Plan
SSAP	Supplemental Statistical Analysis Plan
PK	Pharmacokinetic or Pharmacokinetics
QL2	Global Health Status/Quality of Life Scale Score from the EORTC QLQ-C30
WHODRUG	World Health Organization Drug dictionary

1. Introduction

The purpose of this statistical analysis plan (SAP) is to provide details of the statistical analyses that have been outlined within the protocol for blinatumomab study 20130316 **Amendmend 5 dated 27 August 2019**. The scope of this plan includes the interim analysis, the primary analysis and final analysis that are planned and will be executed by the Biostatistics department or designee unless otherwise specified. The analysis of Health-related Quality of Life endpoints will be described in a separate supplemental SAP (SSAP). PK data analyses will be provided by Clinical Pharmacology Modeling and Simulation group. Exploratory biomarker endpoints will be analyzed in a separate Contributing Scientific Report by scientists from the Clinical Biomarkers and Diagnostics (CBD) group.

2. Objectives

2.1 Primary

- To evaluate the rate of hematological response (complete remission/complete remission with partial hematological recovery [CR/CRh*]) induced by blinatumomab in Chinese adult subjects with relapsed/refractory B-precursor acute lymphoblastic leukemia (ALL).

2.2 Secondary

- To evaluate pharmacokinetics (PK) of blinatumomab
- To evaluate the effect of blinatumomab on overall survival (OS)
- To evaluate the relapse-free survival (RFS) induced by blinatumomab
- To evaluate minimal residual disease (MRD) response induced by blinatumomab
- To evaluate the incidence of allogeneic hematopoietic stem cell transplantation (alloHSCT) and 100-day mortality following HSCT in blinatumomab treated subjects
- To estimate the effect of blinatumomab on patient reported outcomes of global health status/quality of life (QoL) using the European Organization for Research and Treatment of Cancer Quality of Life Questionnaire C30 (EORTC QLQ-C30) (analyses described in a SSAP).

2.3 Safety

- To evaluate the safety of blinatumomab in Chinese subjects with relapsed/refractory B-precursor ALL

2.4 Exploratory

- To evaluate central nervous system (CNS) symptoms and explore potential predictive factors for CNS events associated with blinatumomab

3. Study Overview

3.1 Study Design

This is an open label, single-arm, multicenter phase 3 study to evaluate efficacy and safety of the BiTE[®] antibody blinatumomab in Chinese adult subjects with relapsed/refractory B-precursor ALL.

The study will consist of a screening period, a treatment period, and a follow-up period. Treatment will consist of up to 5 cycles of blinatumomab (for details see Section 6.2.2 of the protocol). Subjects who have achieved a BM response ($\leq 5\%$ BM blasts) or CR/CRh*/CRi within 2 induction cycles of treatment may continue to receive up to 3 additional consolidation cycles of blinatumomab. Thirty days (± 3 days) after end of the last dose of protocol-specified therapy, subjects will have a safety follow-up visit.

Following this, there will be long term (efficacy/survival) follow-up portion of the study for disease status and overall survival. Subjects will be followed via clinic visit or telephone contact every 3 months (± 1 month) after their safety follow-up visit until death has been observed or a maximum of 2 years after start of treatment, whichever occurs first.

If subjects are suitable for alloHSCT after treatment with blinatumomab, they may undergo alloHSCT instead of receiving further consolidation cycles with blinatumomab. It is recommended to administer at least 2 cycles of blinatumomab before alloHSCT. The subjects should complete the safety follow-up visit before undergoing a transplant, and these subjects will continue to be followed in the long term follow-up phase of the study.

In order to enroll representative and balanced adult ALL subjects in terms of the number of prior salvage treatments, the study requires that approximately 50% of subjects are receiving salvage treatment for the first time.

Salvage treatment will be categorized in the interactive voice response system/interactive web response system (IVRS/IWRS) in order to monitor the number of subjects enrolled in each category. Subjects will be categorized to:

- (a) those expecting to receive blinatumomab as a first salvage treatment or
- (b) those expecting to receive blinatumomab as a second or greater salvage treatment.

The overall study design is described by a study schema at the end of the protocol synopsis section.

3.2 Sample Size

The overall sample size of 120 subjects, calculated using the exact method for a single proportion, was estimated in order to ensure 90% power to detect a significant difference in terms of CR/CRh* rate between historical control with 30% CR/CRh* rate and blinatumomab assuming 45% CR/CRh* rate in the alternative hypothesis, at the 2.5% one-sided significance level.

4. Study Endpoints and Covariates

4.1 Study Endpoints

Primary Endpoint

- CR/CRh* rate within 2 cycles of treatment with blinatumomab

Secondary Endpoints

- CR rate within 2 cycles of treatment with blinatumomab
- CR/CRh*/CRi (complete remission with incomplete hematological recovery) rate within 2 cycles of treatment with blinatumomab
- Pharmacokinetic parameters
- Overall survival
- Relapse-free survival
- MRD response rate within 2 cycles of treatment with blinatumomab
- Proportion of subjects undergoing allogeneic HSCT among those who achieved CR/CRh* after treatment with blinatumomab
- 100-day mortality after allogeneic HSCT
- Time to a 10 point decrease from baseline in global health status/Quality of Life (QoL) using the EORTC QLQ-C30.

Safety Endpoints

- Overall incidence and severity of adverse events
- Incidence of anti-blinatumomab antibody formation

Exploratory Endpoints

- **Neurological adverse events**
- Quantification and characterization of peripheral blood lymphocyte subsets
- Quantification and characterization of serum cytokines and chemokines

4.2 Planned Covariates

The following covariates may be used to examine key efficacy and/or safety in subgroups or covariates analyses:

- Sex (female vs. male)
- Age (< 35 vs ≥ 35 to < 55 vs ≥ 55)

- Prior salvage therapy (yes vs. no)
- Prior alloHSCT (yes vs. no)
- Bone marrow blast at baseline (<50% vs. ≥50%)
- Disease status (primary refractory vs first relapse vs second or later relapse)
- Refractory to last previous therapy (yes vs. no)

5. Hypotheses and/or Estimations

The clinical hypothesis is that blinatumomab will have clinically meaningful anti-tumor activity better than 30% as measured by CR/CRh* rate within 2 cycles in Chinese adult subjects with relapsed/refractory B-precursor acute lymphoblastic leukemia. The anticipated CR/CRh* rate of blinatumomab within 2 cycles will be 45%.

6. Definitions

Age

Age will be determined by sites at day 1 of the first infusion of blinatumomab.

AlloHSCT rate

AlloHSCT rate is defined as the proportion of subjects undergoing alloHSCT among whom achieve CR/CRh* after treatment with blinatumomab.

Anti-cancer therapies during long term follow-up

Anti-cancer therapies during long term follow-up will be those therapies entered in the anti-cancer therapy case report form (CRF) administered during the long term follow-up period of the study.

Baseline

For data analyses, baseline will be defined as the value measured on day 1 of the first infusion of blinatumomab. The protocol specifies that all study procedures on day 1 should be completed before the initiation of blinatumomab which will be the assumption in the analysis unless the time of the assessment is recorded. If a day 1 value is not available, the latest value before the day of the start of blinatumomab may be used.

Blast Free Hypoplastic or Aplastic Bone Marrow

Defined as having ≤ 5% blasts in the bone marrow, no evidence of disease, and insufficient recovery of peripheral blood counts: platelets ≤ 50,000/μl and/or ANC ≤ 500/μl.

Complete cycle

A complete cycle is defined as undergoing ≥ 90% of a planned cycle's duration (in days).

Complete Remission (CR)

A CR is defined as having $\leq 5\%$ blasts in the bone marrow, no evidence of disease, and full recovery of peripheral blood counts (platelets $> 100,000/\mu\text{L}$, and absolute neutrophil count [ANC] $> 1,000/\mu\text{L}$). CR rate is defined as the proportion of subjects who achieve CR within 2 cycles of treatment with blinatumomab. Subjects without response assessment will be accounted for in the denominator when calculating the response rate.

Complete Remission with Partial Hematological Recovery (CRh*)

CRh* is defined as $\leq 5\%$ blasts in the bone marrow, no evidence of disease and partial recovery of peripheral blood counts: platelets $> 50,000/\mu\text{L}$, and ANC $> 500/\mu\text{L}$.

Complete Remission with Incomplete Hematological Recovery (CRi)

CRi is defined as $\leq 5\%$ blasts in the bone marrow, no evidence of disease and incomplete recovery of peripheral blood counts: platelets $> 100,000/\mu\text{L}$ or ANC $> 1,000/\mu\text{L}$ (but not both).

CR/CRh*

CR/CRh* is defined as having either CR, or CRh*. CR/CRh* rate is defined as the proportion of subjects who achieve CR/CRh* within 2 cycles of treatment with blinatumomab. Subjects without response assessment will be accounted for in the denominator when calculating the response rate, ie, these subjects will be counted as non-responders.

CR/CRh*/CRi

CR/CRh*/CRi is defined as having either a CR, CRh*, or CRi. CR/CRh*/CRi rate is defined as the proportion of subjects who achieve CR/CRh*/CRi within 2 cycles of treatment with blinatumomab. Subjects without response assessment will be accounted for in the denominator when calculating the response rate.

Cumulative Dose of Blinatumomab

Blinatumomab: The cumulative dose in μg is defined as the following with summation over infusions:

$$\sum \text{duration of infusion [days] for each dose received} \times \text{dose received} [\mu\text{g/day}]$$

Cumulative dose will be calculated within a cycle and across all cycles.

Death Date

For subjects who die during the study, the death date will be recorded on the end of

study CRF as the end of study date. For deaths collected after a subject has ended study (eg, through public records or as part of adverse event (AE) reporting post end of study date), the death date will be recorded on the long term follow-up CRF in the subject status date or on the AE CRF in the AE end date for a grade 5 AE.

End of Blinatumomab Therapy Date

The end of Blinatumomab therapy date is the date the decision was made to end investigational product reported on the end of investigational product administration CRF.

End of Study (Primary Completion)

For a subject: a subject ends the study when they die, consent is withdrawn, or they are lost to follow-up. The end of study date will be captured on the end of study CRF.

For the study as a whole: the primary completion date is defined as the date when the last subject is assessed or receives an intervention for the final collection of data for the primary endpoint(s), for the purposes of conducting the primary analysis, whether the study concluded as planned in the protocol or was terminated early. The primary completion date is when data for the primary endpoint are last collected for the purposes of conducting the primary analysis. If the study concludes prior to the primary completion date originally planned in the protocol (ie, early termination of the study), then the primary completion will be the date when the last subject is assessed or receives an intervention for evaluation in the study (ie, last subject last visit).

End of Study

The end of study date is defined as the date when all the last subject across all sites is assessed or receives an intervention for evaluation in the study (ie, last subject last visit), following any additional parts in the study (eg, longterm follow-up), as applicable.

Enrollment Date

The date of enrollment is the date the subject gets first infusion of blinatumomab .

Overall Survival (OS)

OS time will be calculated from the time of first infusion of blinatumomab until death due to any cause. Subjects still alive will be censored at the date last known to be alive up until the data cut-off date.

Relapse event

A relapse event is any one of the following:

- Hematological relapse: proportion of blasts in bone marrow > 5% or blasts in peripheral blood after documented CR or CRh* or CRi
- Extramedullary relapse: extramedullary lesion that is new or increased by 50% from nadir as assessed by Cheson criteria ([Cheson et al, 2007](#))

Relapse-free survival (RFS)

RFS time will be calculated from the first onset of CR/CRh* within the 2 cycles until the documented hematological relapse, extra-medullary disease, or death due to any cause, whichever occurs first. The analysis is restricted to subjects who achieve CR/CRh* within 2 cycles of treatment. The subjects still alive and relapse-free will be censored at the date of last disease assessment up until the data cut-off date. Sensitivity analyses of RFS will be calculated similarly for those who achieve CR/CRh* and those who achieve CR/CRh*/Cri at anytime during the study.

Last Dose Date of Blinatumomab:

The stop date of the last infusion of blinatumomab administered.

MRD Response

MRD response is defined as favorable if MRD < 1×10^{-4} leukemic cells detectable measured by flow cytometry, within 2 cycles of blinatumomab treatment. The presence of a low number of leukemic cells that are not detectable by light microscopy after induction therapy and/or consolidation therapy is an independent prognostic factor for poor outcome of ALL. Subjects whose MRD persists during induction and consolidation of front-line treatment or who become MRD-positive following treatment, have a poor leukemia free survival.

MRD response rate is defined as the proportion of subjects who achieve MRD response within 2 cycles of treatment with blinatumomab among subjects who achieved CR/CRh* within 2 cycles of treatment with blinatumomab and had evaluable MRD assessment.

Percent of Intended Dose of Blinatumomab:

For a given cycle, the percent of intended dose of blinatumomab will be the cumulative dose in that cycle divided by the planned cumulative dose for that cycle. For the first cycle, the planned cumulative dose will be $(9 \mu\text{g}/\text{day} \times 7 \text{ days}) + (28 \mu\text{g}/\text{day} \times 21 \text{ days}) = 651 \mu\text{g}$. For subsequent cycles, the planned cumulative dose will be $(28 \mu\text{g}/\text{day} \times 28 \text{ days}) = 784 \mu\text{g}$. For the entire study, the percent of intended

dose of blinatumomab will be the sum of the cumulative doses across cycles divided by the sum of the planned cumulative doses across the cycles started. Re-started cycles will have the planned cumulative dose counted both for the period before the re-start and for the period after the re-start in the calculation of the percent of intended dose.

Prior Salvage Regimens

Prior salvage regimens are those medications recorded on the prior anti-cancer therapies CRF where the line of therapy field indicates salvage chemotherapy.

Protocol-specified Therapy

Protocol-specified therapy refers to the treatment blinatumomab. The protocol also uses the term “protocol required therapy” but for consistency protocol-specified therapy will be used throughout this document.

Relative Treatment Duration of Blinatumomab:

For each cycle, the relative treatment duration will be duration of blinatumomab infusion for that cycle divided by 28 days, the planned duration of infusion. For the entire study, the relative treatment duration will be the duration of blinatumomab infusion for the entire study divided by 28 times the number of cycles started. Re-started cycles will count as 28 days for the period before the re-start and 28 days for the period after the re-start in the calculation of planned duration.

Study Day 1

The first day of the infusion of blinatumomab.

Treatment-emergent Adverse Event

AEs starting on or after first dose of blinatumomab as determined by the flag indicating if the adverse event started prior to the first dose on event page of CRF and up to and including 30 days after the end of blinatumomab. This reporting window also applies to treatment-emergent serious adverse events (SAEs).

7. Analysis Sets

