CR/CRh*	81	(42.9%)	(35.7%-50.2%)
CR ^a	63	(33.3%)	(26.7%-40.5%)
CRh* ^b	18	(9.5%)	(5.7%-14.6%)
Blast free hypoplastic or aplastic bone marrow ^c	17	(9.0%)	(5.3%-14.0%)
Partial remission ^d	5	(2.6%)	(0.9%-6.1%)
Non-responder during the first 2 cycles			
Progressive disease	27	(14.3%)	
Non-response	41	(21.7%)	
No response assessment ^e	18	(9.5%)	

ANC = absolute neutrophil count; BM = bone marrow; CI = confidence interval; CR = complete response; CRh* = complete response with partial recovery of peripheral blood counts; PAS = primary analysis set
^a Bone marrow blasts ≤ 5%, no evidence of disease, and full recovery of peripheral blood counts: platelets > 100,000/μL and absolute neutrophil count (ANC) > 1,000/μL.
^b Bone marrow blasts ≤ 5%, no evidence of disease, and partial recovery of peripheral blood counts: platelets > 50,000/μL and ANC > 500/μL.
^c Less than or equal to 5% blasts in the BM, no evidence of disease, and insufficient recovery of peripheral blood counts: platelets ≤ 50,000/μL and/or ANC ≤ 500/μL.
^d Bone marrow blasts 6% to 25% with at least a 50% reduction from baseline.
^e No response assessment is generally a result of subject withdrawal from treatment due to adverse events.

Approved

The median RFS for subjects who achieved CR/CRh* during the core study was 5.9 months (95% CI: 4.8, 8.3). When based on the best response within the first 2 cycles, the median RFS for subjects who achieved a best response of CR was 6.9 months (95% CI: 4.2 to 10.1 months) (N = 63) and 5.0 months (95% CI: 1.4 to 6.2 months) (N = 18) for subjects who achieved a best response of CRh*.

For subjects who achieved CR/CRh* and had a MRD assessment during the first 2 cycles (N = 73), the MRD response rate was 82.2% (60/73; 95% CI: 71.5% to 90.2%), and the complete MRD response rate was 69.9% (51/73; 95% CI: 58% to 80.1%).

The median OS for all subjects was 6.1 months (95% CI: 4.2, 7.5). For subjects who achieved CR/CRh* and were alive and not censored by day 36 (n = 60), the median OS after day 36 was 11.2 months (95% CI: 7.8, not estimable [NE]). For non-responders who were alive and not censored by day 36 (n = 101), the median OS after day 36 was 3.0 months (95% CI: 2.4, 4). For subjects who achieved CR/CRh* and were MRD negative, the median OS was 11.5 months (95% CI: 8.5, NE).

Safety results from studies MT103-206 and MT103-211:

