If clinical signs of extramedullary lesions are present, assessments will be performed according to Cheson criteria (Table 10). If computed tomography (CT) scans are conducted, this should be done according to standard clinical practice. If a CT scan has been performed within one month before start of blinatumomab treatment and if no clinical signs of a change of disease state have been observed, this assessment can be regarded as screening assessment.

**Table 10. Cheson Criteria for Evaluation of Extramedullary Disease
 (From Cheson et al. 2007)**

Response	Definition	Nodal Masses	Spleen, Liver	Bone Marrow
CR	Disappearance of all evidence of disease	(a) FDG-avid or PET positive prior to therapy; mass of any size permitted if PET negative (b) Variably FDG-avid or PET negative; regression to normal size on CT	Not palpable, nodules disappeared	Infiltrate cleared on repeat biopsy; if indeterminate by morphology, immunohistochemistry should be negative
PR	Regression of measurable disease and no new sites	≥ 50% decrease in SPD of up to 6 largest dominant masses; no increase in size of other nodes (a) FDG-avid or PET positive prior to therapy; one or more PET positive at previously involved site (b) Variably FDG-avid or PET negative; regression on CT	≥ 50% decrease in SPD of nodules (for single nodule in greatest transverse diameter); no increase in size of liver or spleen	Irrelevant if positive prior to therapy; cell type should be specified
SD	Failure to attain CR/PR or PD	
 FDG-avid or PET positive prior to therapy; PET positive at prior sites of disease and no new sites on CT or PET Variably FDG-avid or PET negative; no change in size of previous lesions on CT 		
Relapsed disease or PD	Any new lesion or increase by ≥ 50% of previously involved sites from nadir	Appearance of a new lesion(s) > 1.5 cm in any axis, ≥ 50% increase in SPD of more than one node, or ≥ 50% increase in longest diameter of a previously identified node > 1 cm in short axis Lesions PET positive if FDG-avid lymphoma or PET positive prior to therapy	> 50% increase from nadir in the SPD of any previous lesions	New or recurrent involvement

Abbreviations: CR, complete remission; FDG, [¹⁸F]fluorodeoxyglucose; PET, positron emission tomography; CT, computed tomography; PR, partial remission; SPD, sum of the product of the diameters; SD, stable disease; PD, progressive disease.

MRD response:

MRD < 10⁻⁴ leukemic cells detectable measured by flow cytometry.

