10.4.3 Secondary Efficacy Endpoint

The secondary efficacy endpoints include RFS, CR rate, CR/CRh*/CRi rate, alloHSCT rate, OS, MRD response rate, and time to a 10 point decrease from baseline in global health status/Quality of Life (QoL) using the EORTC QLQ-C30.

- RFS: RFS time will be calculated from the first onset of CR/CRh* within the 2 cycles until the documented hematological relapse, extra-medullary disease, or death due to any cause, whichever occurs first. The analysis is restricted to subjects who achieve CR/CRh* within 2 cycles of treatment. The subjects still alive and relapse-free will be censored at the date of last disease assessment. If the last disease assessment date is after the date that triggers the analysis, the subject will be censored at the analysis trigger date. Sensitivity analyses of RFS will be calculated similarly for those who achieve CR/CRh* and those who achieve CR/CRh*/CRi.
- CR rate within 2 cycles of treatment with blinatumomab: CR rate is defined as the proportion of subjects who achieve CR within 2 cycles of treatment with blinatumomab. Subjects without response assessment will be accounted for in the denominator when calculating the response rate.
- CR/CRh*/CRi rate within 2 cycles of treatment with blinatumomab: CR/CRh*/CRi rate is defined as the proportion of subjects who achieve CR/CRh*/CRi within 2 cycles of treatment with blinatumomab. Subjects without response assessment will be accounted for in the denominator when calculating the response rate.
- AlloHSCT rate: AlloHSCT rate is defined as the proportion of subjects undergoing alloHSCT among who achieve CR/CRh* after treatment with blinatumomab.
- Overall survival (OS): OS time will be calculated from the time of first infusion of blinatumomab until death due to any cause. Subjects still alive will be censored at the date last known to be alive. If the date last known to be alive is after the date that triggers the analysis, the subject will be censored at the analysis trigger date.
- MRD response rate within 2 cycles of treatment of blinatumomab: MRD response rate is defined as the proportion of subjects who achieve MRD response within 2 cycles of treatment with blinatumomab. Subjects without response assessment will be accounted for in the denominator when calculating the response rate.

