- 100 day mortality after alloHSCT: The 100-day mortality after alloHSCT will be summarized with the 100-day KM rate among the subjects who achieve CR/CRh* without intervening therapy after blinatumomab and undergo alloHSCT.
- Time to a 10 point decrease from baseline in global health status/ QoL using the EORTC QLQ-C30: Time to a 10 point decrease will be calculated from baseline to the time of first 10 point decrease in terms of global health status/QoL using EORTC QLQ-C30. Subjects still alive and no occurrence of 10 point decrease will be censored at the date of last assessment of EORTC QLQ-C30. This analysis will be performed on subjects with a non-missing baseline and at least 1 non-missing post-baseline result of any EORTC QLQ-C30 scales/item.

For the time to event endpoints such as RFS , OS, and time to a 10 point decrease from baseline in global health status/Quality of Life (QoL) using the EORTC QLQ-C30, the endpoints will be summarized descriptively with hazard ratio, KM curves, KM quartiles

(when estimable), the number of subjects with events, the number of subjects censored, and the pattern of censoring.

The CR rate, CR/CRh*/CRi rate, alloHSCT rate and MRD response rate will be calculated and the exact binomial 95% confidence interval will be generated for the rates.

The primary analysis will be based on the Primary Analysis Set.

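### The SAP computes the MRD response rate only among CR/CRh* responders with an evaluable MRD result; the protocol defines it over all subjects and keeps the unassessed in the denominator

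*SAP*

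**What the plan says.** **Protocol.** Section 10.4.3 takes the MRD response rate over subjects in general. Its wording for who counts as a responder and who stays in the denominator is: "achieve MRD response within 2 cycles of treatment with blinatumomab. Subjects without response assessment will be accounted for in the denominator". It states no restriction to haematological responders. Where the same section wants such a restriction it says so: for RFS, "The analysis is restricted to subjects who achieve CR/CRh* within 2 cycles of treatment", and the alloHSCT rate is likewise confined to subjects who achieve CR/CRh*. MRD response itself (section 7.2.13) is a level below 10^-4 "leukemic cells detectable measured by flow cytometry".

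**SAP.** The endpoint list in section 4.1 gives "MRD response rate within 2 cycles of treatment with blinatumomab" without qualification. Section 6, under MRD Response, then fixes the denominator as the subjects counted "among subjects who achieved CR/CRh* within 2 cycles of treatment with blinatumomab and had evaluable MRD assessment". That adds two filters: CR/CRh* within 2 cycles, and an evaluable MRD result. In the same section the SAP keeps unassessed subjects in the denominator for CR, CR/CRh* and CR/CRh*/CRi. MRD is the only one of these response rates for which it drops the rule.

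**The concern.** Two analysts, one working from each document, would report different figures for the same named secondary endpoint. The figures also answer different questions. The protocol rate asks how often a treated subject reaches MRD response. The SAP rate asks how deep the remission is in those who reached CR/CRh* and could be measured. If the MRD proportion among responders is stable, the SAP rate does not change whether few or many subjects respond, and a reader could take it for an all-treated result.

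The evaluability filter is not hypothetical. Protocol 7.2.11 says that a core biopsy allows no central MRD assessment, so some responders can be expected to have no result.

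The planned subgroup logistic regressions of MRD response (SAP 10.1 and 10.5.2) inherit the denominator. If 40 of 49 evaluable responders were MRD responders (the projection below, rounded), only 9 non-responders would be spread over seven covariates. Under the protocol definition there would be 120 − 40 = 80.

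**Working it through.** **The two rules side by side**

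| Subject | Protocol 10.4.3 | SAP section 6 |
|---|---|---|
| CR/CRh*, MRD result available | in denominator | in denominator |
| CR/CRh*, no MRD result | in denominator, not a responder | excluded |
| No CR/CRh*, MRD response (e.g. blast-free marrow) | in denominator, a responder | excluded |
| No CR/CRh*, no MRD response or no result | in denominator, not a responder | excluded |

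**Inputs**, all from Protocol 2.5.2 (MT103-211) unless noted
- Treated subjects: 189. CR/CRh* within 2 cycles: 81.
- CR/CRh* with an MRD assessment: 73. MRD responders among them: 60.
- Blast-free hypoplastic or aplastic marrow: 17 (Table 6). Their MRD results are not reported.
- This trial: N = 120 and anticipated CR/CRh* rate 45% (Protocol 10.2).

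**Step 1. Reproduce the documents' figure.** 60/73 = 82.2%, Clopper-Pearson 95% CI 71.5% to 90.2%. This matches the protocol and has the SAP's type of denominator.

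**Step 2. Same data, other denominators** (Clopper-Pearson 95% CI)

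| Denominator | Rate | 95% CI |
|---|---|---|
| CR/CRh* with MRD result (SAP) | 60/73 = 82.2% | 71.5–90.2 |
| All CR/CRh*, missing counted as failure | 60/81 = 74.1% | 63.1–83.2 |
| All treated, no other MRD responders | 60/189 = 31.7% | 25.2–38.9 |
| All treated, all 17 blast-free marrows MRD responders | (60 + 17)/189 = 40.7% | 33.7–48.1 |

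The evaluability filter accounts for 82.2 − 74.1 = 8.1 points. The responder restriction accounts for the rest: 74.1 − 40.7 = 33.4 to 74.1 − 31.7 = 42.4 points.

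**Step 3. Project to 120 subjects.** Let r be the CR/CRh* rate.
- Evaluable responders: 120r × 73/81.
- MRD responders among them: m = 120r × 60/81.
- SAP rate: m divided by evaluable responders = 60/73.
- Protocol rate: from m/120 to m/120 + 17/189.

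At r = 0.45, m = 54 × 60/81 = 40 and evaluable responders = 54 × 73/81 = 48.7. The SAP rate is 40/48.7 = 82.2%. The protocol rate runs from 40/120 = 33.3% to 33.3 + 9.0 = 42.3%, a gap of 48.9 to 39.9 points.

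| r | SAP rate | Protocol rate |
|---|---|---|
| 30% | 82.2% | 22.2–31.2% |
| 40% | 82.2% | 29.6–38.6% |
| 45% | 82.2% | 33.3–42.3% |
| 50% | 82.2% | 37.0–46.0% |

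The constant SAP column follows from holding the MRD proportion among responders fixed. It shows what the measure responds to and is not a forecast. The blast-free proportion is also held at 17/189 throughout.

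**Step 4. Vary the MRD proportion c among evaluable responders** (assumed range, because MT103-211 used PCR), at r = 0.45, with m = 48.67 × c
- c = 0.60: m = 29.2; protocol rate 24.3–33.3%; gap 35.7–26.7 points.
- c = 0.90: m = 43.8; protocol rate 36.5–45.5%; gap 53.5–44.5 points.

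**The case against.** The strongest case is that a rate among haematological responders is a recognised way to report MRD. MRD describes leukaemia below microscopic detection, which presupposes morphological remission, and the protocol reports MRD among haematological responders in both earlier studies. Since core biopsies give no central MRD result, an evaluability condition is understandable. SAP section 6 is explicit and reproducible on its own. The endpoint is descriptive, and no decision rule rests on it.

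All of that stands, but it does not reconcile the two texts. Whatever the merits of conditioning on response, the protocol keeps unassessed subjects in the denominator and the SAP removes them.

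Two further points limit the supporting evidence. The protocol's sentence "The primary analysis will be based on the Primary Analysis Set" does not settle the denominator, because the same section covers RFS and the alloHSCT rate, which are responder subsets; the parallel sentence in SAP 10.5.2 has the same limit. The silence of the SAP endpoint list also proves little, since it lists RFS equally without qualification. The finding therefore rests on the MRD definitions in Protocol 10.4.3 and SAP section 6.

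The 40-to-49-point gap is a difference between two quantities, not a bias in either one. Only about 8 points come from the handling of missing results.

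A reason may be recorded in SAP front matter not available here, but Protocol 10.4.3 would still be uncorrected. The SAP is written to protocol Amendment 5, and the stated rationale for Amendment 6 concerns only the primary completion date.

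**Conclusion.** The concern holds. SAP section 6 defines a different quantity from the secondary endpoint in Protocol 10.4.3, and no visible text declares or justifies the change. At the planned 45% CR/CRh* rate the two definitions would give about 82% and 33% to 42%. With the MRD proportion among evaluable responders varied from 60% to 90%, the gap runs from about 27 to 54 points. These figures assume that the MT103-211 proportions carry over despite the change of assay, and that MRD responders outside CR/CRh* number between none and all of the blast-free marrows. The contradiction itself needs no such assumption. MRD response carries no alpha, so the primary test, sample size, power and interim boundaries are untouched. This should be fixed before analysis.

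**What to change.** In SAP section 6, restore the protocol definition:
- **Numerator:** any subject with MRD below 10^-4 by flow cytometry within 2 cycles, whether or not CR/CRh* was reached.
- **Denominator:** the Primary Analysis Set, with a missing MRD result counted as non-response.

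Report the rate among CR/CRh* responders with an evaluable result as a labelled supplementary summary. Show its denominator and the number of responders without an MRD result. State which denominator the subgroup regressions use.

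If the responder-only rate is the intended endpoint, amend Protocol 10.4.3 to say so, including the treatment of unassessed subjects, and give the reason.

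The cost is one SAP definition and one or two table rows, with no new data. The headline MRD figure will be lower than under the present SAP wording, and the two rates must be labelled clearly.
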